14.1.24 Data handling and programming rules

The following section should be used as guidance for development of the protocol, data handling procedures or programming requirements (e.g. on incomplete dates).

14.1.25 Study/project specific decisions

For each study (or project) various issues need to be addressed and specified in the protocol or RAP documentation. Any deviations from protocol must be discussed and defined at the latest in the RAP documentation.

The proposed primary analysis and potential sensitivity analyses should be discussed and agreed with the health authorities and documented in the protocol (or at the latest in the RAP documentation before database lock).

14.1.26 Treatment and study completion CRFs

If study drug is discontinued, the **End of Treatment Page** is to be completed with a visit date reflecting the date the discontinuation decision was made, and with the ‘Last known date patient took study drug’ and one of the following reasons:

- AE(s)
- Abnormal laboratory value(s)
- Abnormal test procedure results(s)
- Protocol violation
- Patient withdrew consent
- Lost to follow-up
- Administrative problems

- Death
- Disease progression
- Treatment duration completed as per protocol (*optional, to be used if only a fixed number of cycles is given*)

For reasons other than progression (and death) it should be checked if this was not in fact progression (especially reasons AEs, Abnormal laboratory value (s), Abnormal test procedure result and patient withdrew consent). Also it should be checked if patient withdrew consent because of safety issues, in which case reasons AEs, Abnormal laboratory value (s), Abnormal test procedure result should be used. In such cases where the reason for discontinuation is AE, the adverse event CRF page must be consistent with the EOT reason provided.

All patients who discontinued study drug will be followed for post a treatment evaluation until progression or until a new anticancer therapy is initiated. Patients who discontinued study drug for reasons other than documented progression, death or lost to follow-up will be followed for progression thereafter (patients who withdrew consent might not be followed with regular tumor assessments at the study site, but should ideally be followed until progression outside the study site). Ideally, all patients who discontinued study drug for progression without documented progression will still be followed with regular tumor assessments (e.g. in case of central radiology review). If patient withdraws consent, it must be clearly stated if patient is also withdrawing consent from post treatment evaluations and/or post treatment follow-up assessments. During that evaluation period, usually only tumor measurements (and/or response status) and survival data are collected. In some protocols, the subsequent anti-cancer therapies may also be recorded.

14.1.27 Study evaluation completion

At the end of the study evaluation period, the **study evaluation completion page** is filled out with the following options:

- Patient withdrew consent
- Lost to follow-up
- Administrative problems (*when follow-up for progression has met protocol required events, e.g. follow-up stopped at certain number of events or certain time*)
- Death
- New cancer therapy (*optional, to be used when follow-up for progression is stopped in this case*)
- Disease progression

Thereafter, patients will be followed for survival using the survival follow-up pages. If information on death becomes available for patients who were lost to follow-up or withdrew consent, this may also be entered in the database. The reason for death must be documented (and will be coded using MedDRA); it must be also stated if death was due to 'Study indication' or 'Other' reason.

In comparative studies with long follow-up period and therefore extended visit schedule, it may be useful to collect the survival status at a pre-specified cut-off within a limited timeframe for all patients with no documented death. In this case, this requires a contact to be made with the

patient or with any reliable source of information on the patient's status, but not requiring a specific visit to be scheduled

Until the specified cut-off point has been reached, the goal is to collect tumor assessments until disease progression for all patients regardless of whether the patients are still receiving study drug. If patients are not followed for progression, e.g. in a Phase I or II study mainly evaluating safety, the evaluation is completed when study drug is completed (in this case only the first completion page is used).

14.1.28 Medical validation of programmed overall lesion response

As RECIST is very strict regarding measurement methods (i.e. any assessment with more or less sensitive method than the one used to assess the lesion at baseline is considered UNK) and not available evaluations (i.e. if any target or non-target lesion was not evaluated the whole overall lesion response is UNK unless remaining lesions qualified for PD), these UNK assessments may be re-evaluated by clinicians at Novartis or external experts. In addition, data review reports will be available to identify assessments for which the investigators' opinion does not match the programmed calculated response based on RECIST criteria. This may be queried for clarification. However, the investigator response assessment will never be overruled.

If Novartis elect to invalidate an evaluation of overall lesion response upon internal or external review of the data, the calculated overall lesion response at that specific assessment is to be kept in a dataset. This must be clearly documented in the RAP documentation and agreed before database lock. This dataset should be created and stored as part of the 'raw' data.

Any discontinuation due to 'Disease progression' without documentation of progression by RECIST criteria should be carefully reviewed. Only patients with documented deterioration of symptoms indicative of progression of disease should have this reason for discontinuation of treatment or study evaluation.

14.1.29 Programming rules

The following should be used for programming of efficacy results:

14.1.30 Calculation of 'time to event' variables

Time to event = end date - start date + 1 (in days)

When no post-baseline tumor assessments are available, the date of randomization/start of treatment will be used as end date (duration = 1 day) when time is to be censored at last tumor assessment, i.e. time to event variables can never be negative.

14.1.31 Incomplete assessment dates

All investigation dates (e.g. X-ray, CT scan) must be completed with day, month and year.

If one or more investigation dates are incomplete but other investigation dates are available, this/these incomplete date(s) are not considered for calculation of the assessment date (and assessment date is calculated as outlined in [Section 14.1.21](#)). If all measurement dates have no day recorded, the 1st of the month is used.

If the month is not completed, for any of the investigations, the respective assessment will be considered to be at the date which is exactly between previous and following assessment. If a previous and following assessment is not available, this assessment will not be used for any calculation.

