7.1.3 Treatment period

INC280 will be dosed continuously on 21-day (3 calendar weeks) cycles beginning on Day 1 of cycle 1. A treatment cycle is defined as 21 days (3 calendar weeks) for the purposes of scheduling procedures and evaluations. There will be no scheduled break between cycles.

Cycles begin on Day 1 of Cycle 1. Visits will occur on Days 1, 2, 15, and 16 of Cycles 1. Days 1 and 8 of Cycles 2. Beginning with Cycle 3 Day 1, scheduled visits will occur every 21 days.

Patients will be treated until one of the following criteria is met:

- Documented disease progression according to RECIST ([Appendix 1](#))
- Unacceptable/intolerable toxicity
- Death or discontinuation from study treatment for any other reason as described in [Section 7.1.4.1](#) and [Section 4.3](#).

Safety and efficacy monitoring should continue as per visit schedule (see [Table 7-1](#) and [Table 7-2](#)). Dose adjustments of study drug (reduction, interruption or) according to safety findings will be allowed. Tumor assessments will be performed at screening, C2D1(± 7 days), then on Day 1 (± 7 days) of every other cycle after C2D1 until disease progression. PR and Complete Response (CR) should be confirmed at the next scheduled tumor assessment (and no sooner than 4 weeks after the initial response).

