7.1.5 Follow up period

30-day follow up

All patients must have safety evaluations for 30 days after the last dose of study treatment.

Patients lost to follow up should be recorded as such in the source documents. For patients who are lost to follow-up, the investigator should show "due diligence" by documenting in the source documents steps taken to contact the patient, e.g., dates of telephone calls, registered letters, etc.

Disease progression follow up

Any patient who discontinues from INC280 for any reason (except for death, disease progression, lost to follow-up, or study termination) will continue to have tumor assessments performed every 6 weeks in the follow-up period until disease progression or start of new anticancer therapy. Patients who withdraw consent to take study treatment but still agree to be followed will continue to have all protocol-specific procedures.

Survival follow up

Upon completion of the 30-day follow up or disease progression follow up, all patients, except those who died, withdrew consent for follow-up as a result of patient decision or were lost of follow-up, will be followed for survival every 3 weeks until death or at least 6 months after last patient first dose.

For patients who transfer to another clinical study or an alternative way to continue provision of study treatment, as described in [Section 4.3](#), the follow-up for safety, disease progression and survival will not be performed.

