10.4.1 Variable

TTP, as per local assessment, is defined as the time from the date of baseline evaluation to the date of the first documented radiological confirmation of disease progression or death due to underlying cancer (RECIST v1.1). If a patient has not had the event at the date of analysis cut-off or when he/she received any further anti-neoplastic therapy, TTP will be censored at the time of the last adequate assessment before the cut-off date.

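### The missing-month rule in 14.1.31 can discard a documented PD scan, because that scan usually has no successor; the resulting informative censoring pushes the TTP estimate upward, rarely and by a small amount

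*Protocol*

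**What the plan says.** Protocol 14.1.31 treats incomplete scan dates in three steps.

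- Where some dates at an assessment are complete ("If one or more investigation dates are incomplete but other investigation dates are available"), the incomplete ones are set aside and the complete ones fix the assessment date.
- Where only the day is missing throughout, the first of the month is used. That is a separate rule and is not at issue here.
- Where the month is missing, "the respective assessment will be considered to be at the date which is exactly between previous and following assessment". The fallback is: "If a previous and following assessment is not available, this assessment will not be used for any calculation".

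Section 14.1.29 introduces these rules with "The following should be used for programming of efficacy results". SAP 2.8 refers to Protocol Appendix 1 for RECIST and sets no scan-date rule. SAP 4.1 handles partial dates only for adverse events, concomitant medication and dosing.

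Tumor assessments on treatment take place on Day 1 "of every other cycle after C2D1 until disease progression" (Protocol 7.1.3). After discontinuation without progression, patients have "tumor assessments performed every 6 weeks in the follow-up period until disease progression or start of new anticancer therapy" (7.1.5). Section 7.2.1 asks for a scan at end of treatment only if none was done in the preceding 30 days. The TTP event in 10.4.1 is the "first documented radiological confirmation of disease progression or death due to underlying cancer". A patient without an event is censored at the last CR, PR or SD assessment, or at first dose if there is no post-baseline assessment (Protocol 10.4.3, SAP 2.7.3).

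**The concern.** Whether the rule keeps a scan depends on whether another scan follows it, and that depends on the result. An SD or PR scan in mid-course has neighbours on both sides and keeps an imputed date. A PD scan with the same defect normally has no successor and is removed. The patient then counts as progression-free up to the previous scan, although progression was documented radiologically.

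The patient's own recorded time becomes shorter, but it changes from an event to a censored time, and the reason for censoring is the event itself. Kaplan-Meier assumes that censoring is unrelated to imminent progression. Here the error runs in the drug's favour on the primary endpoint of a single-arm trial, whose success rule (Protocol 10.8, SAP section 3) requires an observed median TTP of at least 4 months.

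**Working it through.** **1. Which scan is lost.** A midpoint needs both neighbours, so the final scan cannot be dated this way. On the protocol's design, with scans at week 3 and then every 6 weeks, simulation gives the share of last post-baseline scans that are PD scans. It is about 90%, 80%, 75% and 70% for true median TTP of 2.2, 4, 5 and 6 months.

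**2. Direction.** Suppose *n* patients are at risk in a scanning round and *d* progress.

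- Kaplan-Meier multiplies by (n − d)/n. If one PD scan is discarded and the patient is censored at the previous scan, the factor becomes (n − d)/(n − 1). The curve from there on is multiplied by n/(n − 1), a relative rise of 1/(n − 1).
- If instead one patient's final non-PD scan in that round is discarded, the factor becomes (n − 1 − d)/(n − 1), a relative fall of d/[(n − 1)(n − d)].
- The fall divided by the rise is d/(n − d), which is below 1 unless at least half of those at risk progress in the round. Fewer patients are also exposed to it (step 1).

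**3. Reproducing the plan's figures.** Inputs are from Protocol 10.8: exponential TTP; loss rate −ln(0.70)/12 = 0.0297 per month; 1.5 patients per month; analysis 6 months after the last enrolment; a one-sided 90% Brookmeyer-Crowley lower limit. At a true median of 4 months the event rate is ln 2/4 = 0.1733. The expected loss is therefore 0.0297/(0.0297 + 0.1733) = 14.6%, against about 15% stated. With a linear interval and the midpoint convention for the median (10,000 runs), the nine Table 10-2 success probabilities re-run all agree within 2 points. For N = 40 they are 0.496, 0.823 and 0.948 at true medians of 4, 5 and 6 months, against 0.50, 0.82 and 0.95. Expected events agree within 1 in all 16 cells.

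**4. Size.** The documents give no rate of missing months, so the share *q* of scans lost is an assumption. The table gives the large-sample median, interpolated between scans, on the week-3-then-6-weekly schedule.

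| True median | q | All kept | PD scans lost | Shift | Final non-PD scans lost |
|---|---|---|---|---|---|
| 4 | 2% | 4.035 | 4.109 | +0.07 | 4.032 |
| 4 | 5% | 4.045 | 4.228 | +0.18 | 4.037 |
| 4 | 10% | 4.048 | 4.436 | +0.39 | 4.033 |
| 4 | 20% | 4.046 | 4.901 | +0.86 | 4.017 |
| 2.2 | 2% | 2.217 | 2.260 | +0.04 | 2.216 |
| 2.2 | 5% | 2.225 | 2.339 | +0.11 | 2.221 |

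The two errors do not cancel.

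**5. Success probability.** This run used continuous event times, a log-log limit and 3,000 runs per cell (standard error about √(0.25/3000) = 0.009). Its starting values therefore differ slightly from Table 10-2, and only the changes matter.

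- True median 4 months, N = 40: 0.47 with nothing lost, then 0.52, 0.56, 0.64 and 0.75 at q = 2%, 5%, 10% and 20%.
- True median 4 months, N = 25: 0.44, then 0.47, 0.50, 0.56 and 0.65.
- True median 2.2 months: it stays small, reaching 0.018 (N = 25) and 0.008 (N = 40) even at q = 10%.

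**6. Whether anything restores the event.** In Table 14-5, discontinuation for progression without documentation is ignored by default (situation E). Death after two or more missed assessments is censored by default (C2). Death after exactly one missed assessment is an event at the death date (C1), so a cancer death then counts, but later than the scan. Section 14.1.21 uses the discontinuation date for documented clinical deterioration without radiologic evidence, which conflicts with the default for situation E and does not describe this patient.

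**The case against.** **The trigger is narrow.** Complete dates are mandatory. Any other dated investigation at the same assessment supplies the date, and each lesion carries its own scan date (14.1.7). The eCRF has validation checks, and missing values are queried (9.3, 9.4). All of this stands, and it is why the upper rows for *q* are bounds rather than expectations.

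**The rule may not be applied as written.** Section 14.1.24 calls the section guidance, 14.1.34 says standard programs need adapting, and the dataset specifications are not among the documents. This stands in part. Against it, 14.1.29 says that the rules should be used, and nothing supplied overrides them.

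**The fallback could mean that neither neighbour exists.** The wording allows that reading, but with one neighbour the midpoint cannot be computed and no other date is offered.

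**A successor may exist.** Treatment can continue beyond progression case by case (6.2.5), or an end-of-treatment scan may be done. Hence usually, not always.

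**Enrolment was halted and the objective is estimation.** This lowers the stakes for the success rule, but the median TTP and its limits are still to be reported.

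**A reader might infer that one lost PD scan would reverse the verdict.** Data can be constructed in which the median jumps a whole scan interval across 4 months. A version with survival at exactly 0.500 on Day 106 depends on convention, however. Taking the first time at or below 0.5 gives 106/30.4375 = 3.5 months. The midpoint to Day 148 gives Day 127, or 127/30.4375 = 4.2 months, which already passes before any scan is lost. Such examples also put every progression in a round on one day, while 7.1.3 allows ±7 days. The documents supply neither event times nor a missing-month rate to support that inference.

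**Conclusion.** The point holds. Followed literally, 14.1.31 removes a documented progression when its month is missing, no other investigation dates it and no later scan exists. TTP is then biased upward on balance. The median shift is below 0.1 month at an assumed 1–2% of PD scans lost and about 0.2 month at 5%. These figures rest on exponential TTP, the 10.8 accrual and loss assumptions, and the original 6-weekly schedule rather than the 12-weekly one in Table 7-2.

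Three stronger readings are not supported:

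- That the error always lengthens TTP. In a patient without PD, the rule only moves censoring earlier.
- That PFS suffers equally. Under 10.5.1, new antineoplastic therapy or death from any cause is also a PFS event, so many such patients still have one, only later.
- That the rule contradicts 10.4.1. That section defines the event but not how to date it when the month is missing. The defect is that 14.1.31 deals with this case by deletion.

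The expected frequency is low. The reason to act is that the bias favours the drug on the primary endpoint and costs almost nothing to remove.

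**What to change.** Add to Protocol 14.1.31 and to SAP 2.7.3 that an assessment with overall response PD is never discarded for an incomplete date. Keep it as an event, dated as follows:

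1. the recorded visit date for that evaluation number;
2. if that is unavailable, the scheduled assessment date, no earlier than the previous assessment and no later than the earliest subsequent dated record, such as the discontinuation-decision date that the End of Treatment page already carries (14.1.26).

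Do not use a midpoint to last contact or death: it could place progression well after the scan and lengthen TTP itself. Flag each imputed date in the listing, so that the number of affected patients is visible.

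The cost is one sentence in each document and a small programming change, with no new data. The SAP's introduction provides for such changes by amendment before database lock or addendum after it.

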14.1.32 Incomplete dates for last contact or death

All dates must be completed with day, month and year. If the day is missing, the 15th of the month will be used for incomplete death dates or dates of last contact.

14.1.33 Non-target lesion response

If no non-target lesions are identified at baseline (and therefore not followed throughout the study), the non-target lesion response at each assessment will be considered 'not applicable (NA)'.

14.1.34 Study/project specific programming

The standard analysis programs need to be adapted for each study/project.

14.1.35 Censoring reason

In order to summarize the various reasons for censoring, the following categories will be calculated for each time to event variable based on the treatment completion page, the study evaluation completion page and the survival page.

For survival the following censoring reasons are possible:

- Alive
- Lost to follow-up

For PFS and TTP (and therefore duration of responses) the following censoring reasons are possible:

- Ongoing without event
- Lost to follow-up
- Withdraw consent
- Adequate assessment no longer available*
- Event documented after two or more missing tumor assessments (optional, see [Table 14-5](#))
- Death due to reason other than underlying cancer (*only used for TTP and duration of response*)

- New cancer therapy added (*optional; only if the protocol specified that PFS/TPP will be censored at that date*)

* Adequate assessment is defined in [Section 14.1.21](#). This reason is applicable when adequate evaluations are missing for a specified period prior to data cut-off (or prior to any other censoring reason) corresponding to the unavailability of two or more planned tumor assessments prior to the cut-off date. The following clarifications concerning this reason should also be noted:-

- This may be when there has been a definite decision to stop evaluation (e.g. reason='Administrative problems' on study evaluation completion page), when patients are not followed for progression after treatment completion or when only UNK assessments are available just prior to data cut-off).
- The reason "Adequate assessment no longer available" also prevails in situations when another censoring reason (e.g. withdrawal of consent, loss to follow-up or alternative anti-cancer therapy) has occurred more than the specified period following the last adequate assessment.
- This reason will also be used for censor in case of no baseline assessment.

14.2 Appendix 2: Child-Pugh classification of severity of liver disease

Child-Pugh classification system

The CPC is used to assess the severity of impaired hepatic function in patients with liver cirrhosis ([Child 1964, FDA guidance 2003](#)). In general, it is used to determine the risk to a patient with regard to the treatment(s) (e.g. surgery, transplant, medication), and, to suggest the perceived survival of the patient over a period of time.

Hepatocellular carcinoma patients who have Child-Pugh grade A score (5 - 6 points) at the baseline screening are eligible for participating in Study CINC280X2201, provided that the patients meet all other eligibility criteria.

Calculation and interpretation for Child-Pugh scores

The severity of liver disease is based on the CPC criteria, which will be calculated based on clinical findings and laboratory results during the screening period. Five variables are considered (severity of ascites, hepatic encephalopathy, abnormality in serum bilirubin, serum albumin and clotting times). A score (between 1 and 3) is accordingly assigned to each of these factors ([Table 14-6](#)). The sum of the scores provides the Child-Pugh score, which corresponds to a Child-Pugh grade (or Child's grade) of A, B or C ([Table 14-7](#)).

Table 14-6 Child-Pugh score calculation

Variables	Points assigned			Units
	1	2	3	
Total Bilirubin	< 2 (<34)	2-3 (34-50)	> 3 (>50)	mg/dL (μ mol/L)
Serum Albumin	> 35 (>3.5)	28-35 (2.8-3.5)	<28 (<2.8)	g/L (g/dL)
PT (or INR)	< 4 (< 1.7)	4-6 (1.7-2.30)	> 6 (>2.30)	sec (no unit)
Ascites	Absent	Slight	Moderate	no unit
Hepatic Encephalopathy*	None	Grade 1-2	Grade 3-4	no unit

*Grade 0: normal consciousness, personality, neurological examination, electroencephalogram

*Grade 1: restless, sleep disturbed, irritable/agitated, tremor, impaired handwriting, 5 cps waves

*Grade 2: lethargic, time-disoriented, inappropriate, asterixis, ataxia, slow triphasic waves

*Grade 3: somnolent, stuporous, place-disoriented, hyperactive reflexes, rigidity, slower waves

*Grade 4: unrousable coma, no personality/behavior, decerebrate, slow 2-3 cps delta activity

Table 14-7 Child-Pugh score interpretation

Severity (grade)	Child-Pugh Score
A	5 - 6
B	7 - 9
C	10 - 15

References (available upon request)

Child CG, Turcotte JG (1964). Surgery and portal hypertension. In: The liver and portal hypertension. Edited by CG Child. Philadelphia: Saunders:50-64

